4.5.7 TEAR FILM COLLECTION

Tears will be collected by holding a small, disposable, sterile glass tube near the participant's lower lid without touching the surface of the eye. During the procedure, participants will be allowed to blink normally. Tears will be collected from each eye until at least 5ul of basal tears have been collected, or after a maximum of 5 minutes collection time, whichever occurs first. All tear samples will be individually labeled with a study code (no participant names will be on these labels) and frozen until further processing. Tear samples will be analyzed for lipid and anti-inflammatory mediator concentration. Any remaining or resulting chemical combinations will be disposed of using standard laboratory procedures as outlined by the UW Safety Office.

4.5.8 SLIT LAMP BIOMICROSCOPY

The participant will be seated behind a slit lamp and the following will be assessed:

Cornea:

Any current or past corneal observations (such as infiltrates, old scars, etc) will be documented at each visit.

Corneal and conjunctival staining

A sodium fluorescein strip, wetted with a few drops of saline, will be applied to the superior bulbar conjunctiva of both eyes. Staining will be graded using the Efron scale (0 to 4, 0 = normal) while viewing with cobalt blue light through a Wratten no. 12 barrier filter.

Palpebral conjunctival hyperemia and roughness

The redness and roughness of the upper and lower eyelids (tarsal plate zone 2) will be assessed using the EFRON Grading scale (0 to 4, 0 = normal/ uniform satin appearance).

5 MONITORING PROTOCOL ADHERENCE

Guidelines to be included on adherence to visit windows and windows around other data collection points (i.e. subjective ratings). Procedures for monitoring and reporting deviations from the windows described in the protocol.

6 POTENTIAL RISKS AND BENEFITS TO HUMAN PARTICIPANTS

This is a minimal risk study because of the use of marketed products and standard optometric assessments.

Contact lenses in this study will be worn on a daily wear basis, for at least 5 days/week and at least 6 hours/wear day. Adverse events and/ or complications in daily wear of soft contact lenses can occur (eg: inflammation and infection). When contact lenses are worn on a daily wear basis there is a small risk of an adverse event compared to not wearing contact lenses. When contact lenses are worn on an extended wear basis, there is a significantly increased risk of an adverse reaction compared with wearing contact lenses on a daily wear basis. Participants will be wearing their habitual contact lens type in this study, there is no increased risk from wearing the lenses in this study. Due to the daily wear nature of the study, this study considered a non-significant risk study based on United States Food and Drug administration (FDA) and International Standards Organization (ISO) guidelines.

This study involves the use of lifitegrast ophthalmic solution 5% (Xiidra). Multiple previous studies have investigated the use of Xiidra in dry eye patients, with a typical exposure to the drops (2 applications/day) of up to 12 weeks or up to 6 months. In these studies, the most common ocular adverse reactions were eye irritation (18%), eye pain (13%) and instillation site reactions (12%); the majority of ocular adverse

reactions were mild and transient in nature. The most common non-ocular adverse reaction was dysgeusia (14%).

Participants may feel some eye irritation during and after the tear collection procedure. This irritation may be due to contact between the eyelid or lashes and the tip of the capillary tube or due to a temporary decrease in the volume of tears in their eye. In most cases, repeated blinking can alleviate this irritation in a very short period of time.

A dye (fluorescein) normally used for eye exams is being used in this study. Although rare, it is possible that participants may have any allergic reaction to the dye. This could cause discomfort to their eye.

Participants are advised to inform the investigator of any sensitivities to any ophthalmic drops or study products.

Participants may benefit directly from taking part in this study since they are receiving a recently introduced eye drop for treatment of dry eye that may also be used by CL wearers. Findings from this study will help researchers understand the effect of Xiidra when used by contact lens wearers, which might result in improved contact lens comfort. Participation in a study may contribute to scientific research information that may be used in the development of new contact lens products and eye drops.

7 ADVERSE EVENTS

See CORE SOP012_v02 for a description of all adverse events, including management and reporting.

An 'adverse event' (AE) refers to any untoward medical occurrence in a subject administered an investigational product or subjected to an investigational study procedure. Any observations taking place prior to determining that a subject meets all inclusion / exclusion criteria for the study and which are not related to the performed study procedures are not considered an AE. An AE can therefore be any unfavourable and unintended sign, symptom, or disease temporarily associated with the investigational product / study procedure, whether there is a causal relationship or not.

A number of conditions may result in temporary suspension until resolution. These include corneal infiltrates, corneal staining, limbal injection, bulbar injection or tarsal conjunctival abnormalities.

To maintain pharmaco-vigilance, information regarding all AEs, SAEs and pregnancies will be collected during the trial and reported according to local regulations. Clinical information about any adverse event will be collected on the standard CORE adverse events clinical report form. Serious adverse events will be reported within 24 hours to the Office of Research Ethics using their Adverse Event Report Form 106.

CORE will also inform the funding agency, Novartis, of all serious adverse events within 24 hours of becoming aware. Unusual failures in efficacy, reports of drug exposure during pregnancy and reports of study drug misuse or abuse, including initial and follow up reports, arising from the study in subjects exposed to the study drug will be reported to Novartis, as soon as it becomes available, but in any event within fifteen (15) calendar days of becoming aware of such information.

8 DISCONTINUATION FROM THE STUDY

Participants may be discontinued at the discretion of the investigator in consideration of participant safety or protocol compliance, or at discretion of the participant. Participants discontinued from a study will be reimbursed \$20 per hour for their active involvement in the study (including the initial screening visit). Upon discontinuing, a participant will be offered the option of their data being withdrawn from future statistical analysis. The following is a list of possible reasons for discontinuation from the study:

- Screening failure: Participants will be discontinued if they do not meet the inclusion and exclusion criteria outlined in section 4.2.3.
- Unacceptable performance with products to be used in study: Participants may be discontinued if they are unable to achieve acceptable comfort and /or vision with the study products.
- Positive slit lamp finding: Participants may be permanently discontinued from the study depending on the severity of the condition and on the judgement of the investigator.
- Adverse event: If a participant experiences an adverse event during the study they may be discontinued based on the clinical judgement of the investigator.
- Symptoms: If the participant has persistent symptoms they may be discontinued based on the clinical judgement of the investigator.
- Disinterest, relocation or illness: The participant may choose to discontinue due to reasons within or beyond their control.
- Violation of protocol or non-compliance: The participant will be discontinued if they are unable or unwilling to follow the protocol specified visit schedules and/or study procedures.
- Instillation of topical ocular medication: The participant will be discontinued if they elect to use a
 topical ocular medication during the study unless that topical ocular medication is prescribed for a
 limited duration (less than two weeks) to treat a transient condition; in this case the participant
 may remain an active participant (at the discretion of the investigator) after stopping topical ocular
 medication following resolution of the ocular condition).
- Lost to follow-up: The participant will be discontinued if they cannot be contacted and do not return for a final exit visit, and if the investigator has made a reasonable effort to contact the participant for a final study visit.
- Premature termination of the study by CORE or the Office of Research Ethics at the University of Waterloo.

A discontinuation form (ADMIN 3), stating the reason for discontinuation, will be completed, which requires the signatures of both the participant and the investigator except where the participant is lost to follow-up in which case only the signature of the investigator is required.

All discontinuations including their reasons will be included in the final report.

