10 STATISTICAL ANALYSIS AND DATA MANAGEMENT

10.1 STATISTICAL ANALYSIS

All data will be analyzed by CORE at the University of Waterloo. Unmasked data analysis will be conducted using Statistica 13 or later. Descriptive statistics will be provided on information regarding baseline variables (age, sex, refractive error distribution, etc.). For data collected on each eye individually (e.g. biomicroscopy), results of the right eye will be reported unless a difference between right eye and left eye is found. Table 3 lists the primary and other outcome variables and anticipated statistical procedures. All data will be tested for normality of distribution using Shapiro-Wilk tests. Statistical significance will be set at 5%. Superiority testing for the primary outcome variable (i.e. VAS ratings for CL-related discomfort and dryness at 12–weeks vs baseline) will be performed, using a superiority margin of 10 units on the 100-point scale. Additional statistical testing may be applied as required.

Table 4: Statistical procedures

Variable	Analysis	Statistical test
CLDEQ-8 score,	Descriptive statistics	Mean, Standard Deviation
 VAS ratings, Pre-lens non-invasive tear breakup time (PLNITBUT), bulbar and limbal redness, tear inflammatory markers; 	Effect of time on the outcome variables (Comparison between visits)	RMANOVA/MANOVA Mauchly's test of sphericity Huynh-Feldt p values Tukey HSD post hocs Paired t-test
Safety measures (biomicroscopy, visual acuity.)	Descriptive statistics Effect of safety and exploratory variables over time	Mean, Standard Deviation RMANOVA/MANOVA Mauchly's test of sphericity Huynh-Feldt p values Tukey HSD post hocs Paired t-test

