10.2 DATA MANAGEMENT

Data from this study will be retained by CORE for a minimum of 25 years on a password-protected server. After 25 years, data will be disposed of in accordance with the guidelines laid out by the University of Waterloo.

At the completion of the study CORE may provide a copy of the study data to the funding agency, Novartis, when requested. Data will typically be sent using a secure file share system operated by the University of Waterloo called Sendit which uses 128bit (or 256bit) SSL encryption. This system provides a secure way to transfer files when email is not appropriate, whether because of file size, file type or concerns over security. Sendit includes features such as password protection, a restricted time period for download, IP logging and email notification of download. Files may be encrypted prior to transmission upon request. Using this method means that data files are only stored on University of Waterloo servers during the transfer.

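### Section 8 routinely offers everyone who discontinues withdrawal of their data from analysis, with no exception for safety or already collected data, so exclusion can depend on outcome

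*Combined protocol and SAP*

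**What the plan says.** Section 8 (Discontinuation from the study) states: "Upon discontinuing, a participant will be offered the option of their data being withdrawn from future statistical analysis". It attaches no condition on the reason for leaving and does not separate safety from efficacy data, or past from future data. Section 9, on study completion, describes no such offer to completers.

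The same section lists ten possible reasons for discontinuation. Four bear on how the participant is doing on the drops: a positive slit lamp finding, and these three:

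- on complaints that do not settle: "If the participant has persistent symptoms they may be discontinued based on the clinical judgement of the investigator"
- on tolerating the products: "Participants may be discontinued if they are unable to achieve acceptable comfort and /or vision with the study products"
- on safety: "If a participant experiences an adverse event during the study they may be discontinued based on the clinical judgement of the investigator"

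Three other provisions limit the consequences. Section 7 says "information regarding all AEs, SAEs and pregnancies will be collected during the trial and reported according to local regulations". Section 8 ends with "All discontinuations including their reasons will be included in the final report". Section 10.2 says "Data from this study will be retained by CORE for a minimum of 25 years", and section 13.7 repeats that period for records and data.

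Section 10.1 gives the analysis. Table 4 puts the VAS ratings and CLDEQ-8 in one row. A second row, opening "Safety measures (biomicroscopy, visual acuity", covers safety. Both use means, standard deviations, repeated-measures ANOVA and paired t-tests. The section defines no analysis population, no handling of missing data and no sensitivity analysis.

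**The concern.** Leaving the study and leaving the analysis are separate events, and the protocol invites a participant to make both at once. Because some reasons for leaving are poor comfort, persistent symptoms or an ocular finding, the invitation is tied to the quantities the study measures: VAS discomfort and dryness, biomicroscopy and acuity. Valid observations made before the participant left can then drop out for reasons related to their values.

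The design offers no protection. There is no control arm in which the same selection would operate, and no defined analysis set that would make the loss visible. At stake are:

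- the symptom and tolerability ratings taken after the first drop at Visit 2, which even a very early leaver will have on record;
- the week 2 and week 6 VAS and CLDEQ-8 results, which section 2 names as outcomes;
- the Table 4 summaries of biomicroscopy and visual acuity.

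The protocol also does not say how the withdrawal option sits alongside section 7. An adverse event could be reported while the same participant's slit lamp grades are absent from the safety summary.

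**Working it through.** **The plan's own figures.** The documents give no expected discontinuation rate and no expected uptake of the offer. Section 4.2.2 allows up to 55 dispensed with a target of 40 completers. So 55 − 40 = 15 participants, or 15/55 = 27.3%, could leave with the target still met. This is a ceiling on how many dispensed participants could be offered withdrawal under that allowance. It is not a forecast, and not all 15 would leave for tolerability.

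**Formula.** Let n participants have a value at a visit and let k of them withdraw their data. Let D be the difference between the mean change in those k and the mean change in those retained. Then

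mean in all n = mean in retained + (k/n) × D,

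so the analysed mean is off by (k/n) × D. This holds for any mean in Table 4: VAS, CLDEQ-8, biomicroscopy grade or logMAR acuity.

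**Illustration for VAS at week 2 or week 6.** Assumptions, none of them from the documents: all 55 have a value at the visit; retained participants change by −20; those who withdraw data change by 0 (D = 20) or by −10 (D = 10).

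| k | k/55 | Mean in all 55, D = 20 | Overstatement, D = 20 | Mean in all 55, D = 10 | Overstatement, D = 10 |
|---|---|---|---|---|---|
| 3 | 5.5% | −18.91 | 1.09 | −19.45 | 0.55 |
| 5 | 9.1% | −18.18 | 1.82 | −19.09 | 0.91 |
| 8 | 14.5% | −17.09 | 2.91 | −18.55 | 1.45 |
| 15 | 27.3% | −14.55 | 5.45 | −17.27 | 2.73 |

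Worked line, k = 5, D = 20: (50 × −20 + 5 × 0)/55 = −18.18, against −20 once the five are removed. The last row needs every one of the 15 to reach the visit, be reachable for the offer, and accept it.

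**Safety means.** The documents give no expected biomicroscopy or acuity values, so only the fraction can be stated: the summary shifts by 5.5%, 9.1%, 14.5% or 27.3% of whatever difference exists between those withdrawn and those retained.

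**The 12-week primary comparison.** A paired test of Day 84 against baseline needs a Day 84 value. A participant who left earlier has none and is omitted whether or not the offer is accepted, so the rule adds little here. A complete-case repeated-measures ANOVA across all visits would omit the same people at weeks 2 and 6 as well. The rule therefore acts through the visit-wise descriptive statistics, the paired tests at weeks 2 and 6, the post-drop ratings at Visit 2 and the safety summaries.

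**The case against.** The strongest reply is that the rule is narrower than it looks and that other sections cover what matters most. Much of that stands.

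- **Deletion.** A reader might infer that data are destroyed. Section 8 speaks only of removal from future statistical analysis, and sections 10.2 and 13.7 keep study data and records for at least 25 years.
- **Adverse event rates.** A reader might take the 18% eye irritation figure in section 6, expect about 10 of 55 (0.18 × 55 = 9.9), and conclude that five withdrawals would turn 10/55 = 18.2% into 5/50 = 10.0%. The documents do not support this. Section 7 reports all adverse events with no exception for withdrawn data, section 8 reports every discontinuation with its reason, and the Table 4 safety row names biomicroscopy and acuity, not event incidence. The 18% also comes from dry eye studies, not from this population.
- **Primary result.** A reader might infer that the 12-week superiority test is inflated. As shown above, early leavers are missing from it anyway. The lack of an analysis set and a missing-data rule is a separate gap, which changing this sentence would not close.
- **Contradiction with section 7.** Reporting events and including data in an analysis are different processes, and both rules can be followed. What is missing is a statement of how they fit together.
- **Who leaves.** Six of the ten reasons, such as relocation or loss to follow-up, are not tolerability or clinical findings, and someone lost to follow-up cannot readily be offered anything.
- **Ethics.** The consent letter is not available here and the study is bound by Tri-Council policy. The offer may be required, so its outright removal cannot be assumed acceptable.

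What the reply does not answer is that graded findings, acuity and symptom scores already collected can leave the analysis through a routine prompt, and that no section keeps them in or requires uptake to be reported.

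**Conclusion.** The point holds in a limited form. Section 8 permits outcome-dependent exclusion of already collected data from the Visit 2 post-drop ratings, the week 2 and week 6 symptom results, and the biomicroscopy and acuity summaries. The risk runs in the drug's favour if those who accept the offer did worse than those retained. That is plausible from the listed reasons but not certain.

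On the assumed differences of 10 and 20 VAS units, an early-visit mean would be overstated by between 0.55 units (3 withdrawals, difference 10) and 5.45 units (15 withdrawals, difference 20). With few acceptances the effect is small. The true size rests on uptake and on how different those participants are, and the documents give neither. It should be corrected, because the remedy is short and the loss cannot be assessed afterwards if uptake is not recorded.

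**What to change.** In section 8, state that data collected up to discontinuation stay in the analysis and that discontinuing stops only further collection. As far as the ethics office requires a right to withdraw data:

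- honour it when the participant asks, not as a routine offer;
- exclude safety data and the reason for discontinuation from it, where ethics rules allow;
- report how many participants used it, when, and their reasons for discontinuing.

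Add a sentence saying how the right relates to adverse event reporting in section 7 and to the Table 4 safety summaries. The reasons for which participants may be discontinued are not touched.

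The cost is a short edit to section 8, matching consent wording and ethics review of that change. The outcome of that review cannot be judged from these documents.

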4.4.7 STUDY EXIT

The Study Exit form must be completed when a participant exits the study. This will occur either at study completion or if the participant is discontinued from the study at another time. A Study Exit form must be completed for all participants who have been allocated a study ID number. Post-study follow-up visits will be scheduled if the investigator determines this is necessary and the exit form will be signed after the last follow-up visit.

At the Study Exit Visit the following details are required:

- Visual acuity with habitual lenses, spectacles or refraction (logMAR);
 - If the VA at the Exit Visit is two or more lines worse than at baseline, the investigator will be required to provide an explanation and complete an adverse event form.

• Post-study follow-up requirement (Y/N): If yes, the reason and date of the follow-up visit must also be recorded.

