4.5 STUDY PROCEDURES

Table 2 summarizes the procedures at each visit. The order of procedures is described in sections 4.4.1 to 4.4.7.

Table 2: Summary of procedures to be conducted at scheduled visits

Procedure	Screening	Baseline/ Dispense	Day 14	Day 42	Day 84
Informed consent	X				
Participant demographics	X				
Contact lens history	X				
Comfortable & Total CL wear time	X	×	x	×	X
Medical history and medications	Х				
Changes in medical history/medications		×	x	×	X
Compliance (Study drops & CL wear)			x	X	X
CLDEQ8	X	X	x	X	X
Symptoms via Young's criteria ⁶	X				
Subjective Ratings (Visual Analog Scales) ^{4,5}	х	х	х	х	X
HCVA (logMAR)	Х	х	х	X	X
PLNITBUT		х	х	х	Х
Lens performance (fit & wettability)	Х	X	x	х	X
Bulbar & limbal redness (Efron & K5M)	X	X	x	×	X
Lens removal	X	X	x	X	х
Tear collection		X	х	X	х
Biomicroscopy	х	х	х	х	X
Xiidra study drop application		х			
Study product dispense (drops & CL/solution)		×	x	×	х
Study product collection					х

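### Participants can be removed for persistent symptoms or poor comfort, the Day 84 comparison then omits them, and no symptom rating is listed for an exit between scheduled visits

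*Combined protocol and SAP*

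**What the plan says.** Section 2 makes the VAS ratings of discomfort and dryness at 12 weeks, against baseline, the primary outcome. Section 10.1 tests them against a superiority margin of 10 units, naming repeated-measures ANOVA and paired t-tests. It gives no analysis set, missing-data method or sensitivity analysis.

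Two of the discontinuation grounds in section 8 concern symptoms: "If the participant has persistent symptoms they may be discontinued based on the clinical judgement of the investigator" and "Participants may be discontinued if they are unable to achieve acceptable comfort and /or vision with the study products". Neither has a threshold or a duration. Section 8 also provides: "Upon discontinuing, a participant will be offered the option of their data being withdrawn from future statistical analysis". All discontinuations and their reasons go into the final report.

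Section 4.4.7 applies to early leavers as well as completers. Of the exit form it says: "This will occur either at study completion or if the participant is discontinued from the study at another time". The details it requires are visual acuity and whether post-study follow-up is needed. The procedures grid is titled "Table 2: Summary of procedures to be conducted at scheduled visits" and has no early-exit column. Section 4.4.6 lists no ratings for unscheduled visits, although data recorded there are entered into the database. Section 4.5.2 asks for the VAS at each study visit and the CLDEQ-8 at every visit. Section 4.4 counts five study visits, and a separate early exit is not among them.

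**The concern.** Everyone enters with an eye dryness score of at least 40 and a dry classification on the Young grid (section 4.2.3). In such a cohort, a participant who does not respond is likely to be one with persistent symptoms, so these grounds for removal lie close to treatment failure. The decision rests with an investigator in an open-label study.

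A paired Day 84 comparison drops anyone without a Day 84 value, and with one arm there is no comparison group in which selective loss would show. If leavers improved less than stayers, the reported change is too large; if they did no worse, there is no such bias. The reported reasons for leaving will show that people left, but not how they rated their eyes when they did. Section 4.2.1 says that the data may be used to size later studies, so an inflated change could carry forward.

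**Working it through.** **Inputs from the documents.** Up to 55 dispensed and a target of 40 completers (section 4.2.2); margin of 10 units (section 10.1). The target of 40 cannot be reproduced, because section 4.2.1 gives no effect size, SD or power. If 55 are dispensed and 40 complete, 15 are lost for all reasons together: 15/55 = 27%.

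**Assumptions.** The documents do not say how many would leave on symptom grounds or how they would rate. Let *k* be the number lost and *gap* the mean improvement in stayers minus that in leavers. I take *k* = 5 and 15, and a gap of 5 to 20 units.

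**Overstatement** = mean in stayers minus mean in all dispensed = *k*/(40 + *k*) × gap.

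| *k* lost | Fraction | Gap 5 | Gap 10 | Gap 20 |
|---|---|---|---|---|
| 5 | 5/45 = 0.111 | 0.6 | 1.1 | 2.2 |
| 15 | 15/55 = 0.273 | 1.4 | 2.7 | 5.5 |

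**Break-even against the margin.** If leavers on average did not change, the mean in all dispensed is the stayers' mean × 40/(40 + *k*). It falls below 10 when the stayers' mean is below:

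- 5 lost: 10 × 45/40 = 11.25 units
- 15 lost: 10 × 55/40 = 13.75 units

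If leavers worsened, the break-even is higher. With 40 stayers improving by 15 and 15 leavers worsening by 5 (a gap of 20), the overall mean is (600 − 75)/55 = 9.5.

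**Effect on the test.** A simulation of 55 participants (4,000 runs) assumed a true mean improvement of exactly 10, an SD of change of 20, and a correlation of 0.3 to 0.5 between improvement and staying in. It tested stayers only against the margin at one-sided 2.5%.

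- 5 lost: bias 1.0 to 1.8 units, false success 6% to 9%.
- 15 lost: bias 2.7 to 4.5 units, false success 13% to 32%.
- Loss unrelated to improvement: bias about 0, false success close to the nominal 2.5%.
- True improvement of 5 instead of 10, 15 lost: false success 0.5% to 1.7%.

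With 15 lost, those biases correspond to gaps of 2.7 × 55/15 = 9.9 and 4.5 × 55/15 = 16.5 units, inside the assumed range. The last line shows that the risk is concentrated near the margin.

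**Where a rating could be missing.**

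| Exit | Symptom ratings |
|---|---|
| At Day 14 or Day 42 visit | CLDEQ-8 and VAS come before lens removal and slit lamp (sections 4.4.3, 4.4.4), so normally already taken |
| Between visits, exit visit attended | Not listed in 4.4.7, 4.4.6 or Table 2; 4.5.2 may or may not apply |
| No exit visit attended | None at exit; only earlier ratings, if any |

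In every row, earlier ratings can also be lost if the participant withdraws their data.

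**The case against.** The text can be read more generously. Section 8, on loss to follow-up, uses final exit visit and final study visit for the same thing, section 4.4.7 speaks of an exit visit, and section 4.5.2 asks for the CLDEQ-8 at every visit. The list in 4.4.7 also governs exit at completion, where both ratings are certainly taken although it does not name them, so its silence proves little. This stands. A reader might infer that leavers will have no symptom data, and the documents do not support that. What remains is that no section says the ratings are due at an exit between visits, and sites could read it either way.

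The size is all assumption, and 15 is a ceiling that includes relocation and illness. The test also gives some protection. With 40 completers, passing it needs an observed mean of about 10 + *t* × SD/√40. At one-sided 5% (*t* = 1.685) that is 14.0 for an assumed SD of 15 and 15.3 for an SD of 20; at two-sided 5% (*t* = 2.023) it is 14.8 and 16.4. All exceed 13.75, so if leavers did not change, a passed test at an SD of 15 or more leaves the overall point estimate above 10. That is correct, but it concerns the point estimate and not the test in all dispensed. It also fails if leavers worsened, as in the 9.5 example.

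A reader might also infer that the compliance ground needs softening. It says "The participant will be discontinued if they are unable or unwilling to follow the protocol specified visit schedules and/or study procedures", while the opening of section 8 says "Participants may be discontinued at the discretion of the investigator in consideration of participant safety or protocol compliance". That ground is different from the symptom grounds, and making it discretionary would add unmasked judgement. I would leave it.

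**Conclusion.** The point holds as a risk of selective loss. Removal for persistent symptoms or unacceptable comfort overlaps with the primary outcome, the Day 84 comparison leaves those participants out, and a final rating is not clearly required when the exit falls between scheduled visits. The direction is toward benefit only if leavers did worse than stayers. A reader might infer that the 12-week change will be inflated; nothing in the documents shows that.

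The size is unknown. The 5.5-unit overstatement needs both extremes, 15 lost and a gap of 20. Across the assumed range, a result well clear of the margin is not threatened. The change is worth making because an exit rating that was not taken cannot be recovered later. It is a cheap improvement and does not affect the validity of the design.

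**What to change.** - **Section 4.4.7 and Table 2:** add an early-exit entry requiring VAS and CLDEQ-8 at any attended early exit visit, before lens removal where possible. Record that day's lens wear time and any rewetting-drop use.
- **Section 10.1:** keep the Day 84 analysis as planned. Add one sensitivity analysis of all dispensed participants whose data are not withdrawn. For leavers, use the early-exit rating, or else the last Day 14 or Day 42 rating. For those with no rating after baseline, assume no change. Report how many withdrew their data and how many have no rating after baseline.

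The cost is one line, one table column and one extra analysis. Both instruments are already in use and no visit is added.

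The limits should be stated with the result. An early-exit rating is not a 12-week rating and may follow less than 6 hours of wear. Participants who do not attend an exit visit will still have no final rating. Assuming no change is not the worst case if some of them worsened.
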